Tranexamic acid (TA, Cyclokapron®) is an FDA-approved anti-fibrinolytic agent for the treatment or prevention of bleeding in bleeding disorders. It is an intravenous agent supplied as a sterile, unpreserved, colorless solution administered in single-dose polymeric bags containing 1000 mg tranexamic acid in sodium chloride in 100 ml and given at a rate of 1 ml/ minute, at 1 g within 3 hours after delivery.

Trial Arms	
Arm A	rVWF 80 IU/kg at delivery (or epidural), and day 1, 2 plus TA 1 gm IV within 3 hours after delivery
Arm B	rVWF 80 IU/kg at delivery (or epidural) and day 1, 2 alone

Study Duration:

[figure not shown]
This is a 8-week inpatient trial in which all subjects will be randomized to one of two treatment arms and followed for 4 weeks.

PROTOCOL SCHEMA

Screening
Week -4
Visit 1

Subjects will be screened at 32-39 weeks' gestation, after signed, informed consent, by inclusion and exclusion criteria; undergo a history, vital signs, and baseline labs: hemoglobin, hematocrit, platelets, Fe, TIBC, ferritin, VWF assays (VWF:RCOF, VWF:Ag, FVIII:C), fibrinogen, and d-dimer, and be randomized to one of two treatment arms.

[figure not shown]
Admission
Childbirth
Week 0
Visit 2

Week 0
Day 0-2
Visits 3-4

On admission for childbirth, subjects will have baseline blood counts, VWF assays, and d-dimer drawn and receive the initial study intervention at delivery (or epidural), and on days 1 and 2 postpartum. At 1 day and 2 days postpartum, lochial blood loss by PBAC, blood products, transfusion, and concomitant medications will be reviewed; and blood counts, VWF assays, fibrinogen, and d-dimer will be drawn.

Week 3
Visit 5

ABSTRACT

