3.2 Research Design and Methods

This is an 8-week, randomized, open-label trial to evaluate the hemostatic efficacy of rVWF plus TA vs. rVWF alone to prevent postpartum hemorrhage, measured by quantitative blood loss (QBL) at delivery in women with VWD. We hypothesize that while rVWF is a hemostatic agent indicated for prevention and treatment of bleeding, including surgical bleeding and delivery, the physiologic fibrinolysis that occurs within three hours of delivery may contribute to an enhanced bleeding tendency in women with VWD and to their greater risk of PPH. We therefore propose to use tranexamic acid, an antifibrinolytic agent, together with rVWF to determine if the combination reduces PPH. It is anticipated that 20 subjects who meet eligibility criteria will enroll in and complete this study. All aspects of this study, including the rVWF infusion, screening, biologic effects study by von Willebrand tests (VWD profile), are considered experimental. This pilot study is an inpatient and outpatient study and will last up to 2 years. The duration of the study for each subject will be up to 8 weeks. With the exception of the screening visit (32-39 weeks' gestation) and the final visit (day 21 postpartum) at either the Hemophilia Center of Western PA (HCWP) or Magee Outpatient Clinic, the study will be performed while the subject is an inpatient at Magee Women's Hospital.

Based on the established safety and efficacy of rVWF in individuals with VWD including pregnant women and at childbirth,^{34,35} and very low rate of thrombosis, 0.4%, based on 570 patients in 13 studies,³⁶ and the established safety and efficacy of TA in surgery,¹¹ trauma,¹² and childbirth,¹³ it is anticipated that the proposed doses will be safe and well-tolerated, with no thrombosis, allergic reaction, or adverse effects.

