The goal of the current study will be to obtain preliminary information on the safety and efficacy of rVWF given at 80 IU/kg at delivery and day 1, day 2, with or without TA 1 gm IV within 3 hours of delivery in reducing postpartum hemorrhage in 20 pregnant VWD subjects. If the study recruitment, randomization, drug administration, data collection and management are feasible, then the large, multicenter phase III trial will be initiated. As both drugs are FDA-approved and have been previously used in VWD patients without adverse effects, we anticipate none during the study. If any subject experiences any grade 3 or higher treatment-related toxicity, blood loss, allergic reaction (fever, chills, hives, tachycardia, chest discomfort), or thrombosis, the decision to continue the study will be made by a local Data Safety Monitoring Committee.

DOSING SCHEMA

Study Arms	No. Subjects	Study Drug(s) at Delivery	Study Drug Postpartum
Arm A	10	rVWF 80 IU/kg + TA 1 gm	rVWF 80 IU/kg days 1 and 2
Arm B	10	rVWF 80 IU/kg	rVWF 80 IU/kg days 1 and 2

rVWF is a single-dose IV infusion given over 5-10 minutes. TA is a single-dose IV infusion given over 10 minutes.

Screening Procedures. Following informed consent, subjects will be screened at the Hemophilia Center of Western PA, by medical history, physical examination, vital signs (height, weight, blood pressure, respirations, heart rate, temperature), and baseline laboratory studies within 3 weeks of the escalating dose study. Baseline labs will include **VWF assays** (VWF:RCo, VWF:Ag, FVIII:C); **coagulation tests** (fibrinogen, d-dimer), **blood counts** (hemoglobin, hematocrit, platelet count); and **iron tests** (Fe, TIBC, ferritin). All tests will be drawn at screening (32-39 weeks' gestation), and all tests except for the iron tests will be drawn on admission for childbirth, at day 1, day 2, and day 21 postpartum. Blood draws will be performed on day 0 pre-delivery by the Magee Labor and Delivery unit as soon as the IV is started. Subsequent blood draws on day 1 and day 2 will be coordinated through HCWP research team. The total blood draw is 49 cc (~2.5 tbsp), including 13 cc (~1 tbsp) at screening; and 9cc (~0.6 tbsp) at the remaining 4 blood draw draws. See Appendix 1.

Up to 30 subjects will be screened to assure 20 subjects are enrolled. Subjects will be randomized to rVWF + TA vs. rVWF alone at delivery. Subjects will receive only the study drug(s) to which they are

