Laboratory Assays. One blue top (5.0 cc) will be obtained for VWF assays: VWF ristocetin cofactor by platelet aggregometry, VWF antigen by ELISA, FVIII activity by chromogenic assay on an ST4 analyzer; and coagulation assays: fibrinogen by Clauss method, and d-dimer by quantitative assay run in the ITxM/Vitalant Coagulation Laboratory, Pittsburgh. One purple top (4.0 cc) will be drawn for blood counts (hemoglobin, hematocrit and platelets), and one SST tube (4.0 cc) will be drawn for iron studies (iron, TIBC, and ferritin) to be run by standard methods at UPMC University Clinical Laboratories.

Study Termination. A subject will be terminated from the study if any of the following situations arise: the subject develops grade 3 or higher toxicity, allergic reaction, or thrombosis at any time during study.

Study Visit 1: Screening, 32-39 Weeks' Gestation

This visit will take place prior to infusion of study drug(s) in order to confirm eligibility requirements. The following tests or assessment will be performed at the Screening Visit.

- The PI, [name] or a co-investigator will discuss the study with potential study subjects, answer questions and assure there is adequate time for the potential subject to decide to participate in the study. The potential subject may sign consent or take the consent with them to discuss with family members or other members of the healthcare team. If the potential subject is interested in participating in the study, she may sign the consent document.
- Medical history will include age, all medical diagnoses, current medications, any allergies.
- Vital signs will include blood pressure, temperature, respirations, pulse, weight and height
- Blood draw: a 13 ml (1 tbsp) plasma sample for blood counts and iron studies by UPMC University Clinical Laboratories; and VWF assays and coagulation tests by the ITxM/Vitalant Coagulation Laboratory, Pittsburgh.
- The subject will be randomized and informed of the group to which she is randomized.

Study Visit 2: Admission for Childbirth

This visit begins on admission for childbirth.

- Interim medical history, new diagnoses, medications, allergies.
- Blood draw: a 9 ml plasma sample for blood counts at UPMC University Clinical Laboratories, and VWF assays and coagulation tests by the ITxM/Vitalant Coagulation Laboratory, Pittsburgh.

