- Study subject will receive study drug(s) to which they are randomized. Arm A subjects will receive rVWF plus TA, while Arm B subjects will receive rVWF alone. The rVWF is given immediately before epidural or delivery, which is first. TA is given within 3 hours of delivery. If bleeding continues after 30 minutes of the first TA dose (in Arm A), a second dose of TA 1 gm IV will be given.
- Quantitative blood loss (QBL) during C-section and vaginal delivery will be calculated by the labor suite nurse and the mode of delivery will be obtained from hospital medical chart.
- Assessment for adverse events, allergic reactions, thrombosis, other bleeding
- The study subject will be given a Diary, to record lochia blood loss by pictorial blood assessment chart (PBAC), blood products, transfusion, and concomitant medications daily for up to 21 days.

Study Visit 3: Day 1 Postpartum

The visit occurs at 1 day postpartum.

- Blood draw: a 9 ml plasma sample for blood counts at UPMC University Clinical Laboratories, and VWF assays and coagulation tests by the ITxM/Vitalant Coagulation Laboratory, Pittsburgh.
- Interim medical history, new diagnoses, medications, allergies.
- Diary review: lochia blood loss by PBAC, blood products, transfusion, and concomitant medications.
- Assessment for adverse events, allergic reactions, thrombosis, other bleeding

Study Visit 4: Day 2 Postpartum

The visit occurs at 2 days postpartum.

- Blood draw: a 9 ml plasma sample for blood counts at UPMC University Clinical Laboratories, and VWF assays and coagulation tests by the ITxM/Vitalant Coagulation Laboratory, Pittsburgh.
- Interim medical history, new diagnoses, medications, allergies.
- Diary review: lochia blood loss by PBAC, blood products, transfusion, and concomitant medications.
- Assessment for adverse events, allergic reactions, thrombosis, other bleeding

Study Visit 5: Day 21, End of Study Visit

The visit occurs at 21 days postpartum, at the end of study.

- Blood draw: a 9 ml plasma sample for blood counts at UPMC University Clinical Laboratories, and VWF assays and coagulation tests by the ITxM/Vitalant Coagulation Laboratory, Pittsburgh.
- Interim medical history, new diagnoses, medications, allergies.
- Diary review: estimated lochia blood loss by PBAC, blood products, transfusion, and concomitant medications.

- Assessment for adverse events, allergic reactions, thrombosis, other bleeding.

The blood volume for all tests is 49 cc (~3 tbsp) during this 8-week trial.

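### Each woman is told her arm at screening, about 4 weeks before the arms differ, creating an avoidable risk of arm-related withdrawal and of bias in recorded blood loss

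*Combined protocol and SAP*

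**What the plan says.** Section 3.2, Study Visit 1, places both allocation and disclosure at the screening visit: "The subject will be randomized and informed of the group to which she is randomized". The protocol schema gives the window for that visit: "Subjects will be screened at 32-39 weeks' gestation, after signed, informed consent". The schema and the Appendix (Schedule of Events) label the visit Week -4, and the Appendix marks randomization there. The Screening Procedures text in section 3.2 is worded differently: "Subjects will be randomized to rVWF + TA vs. rVWF alone at delivery".

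The trial is described as open-label in sections 1.0 and 3.2. The rVWF dose and days are identical in the two arms. The one difference is TA in Arm A, which the Trial Arms table places after delivery and Study Visit 2 describes as follows: "TA is given within 3 hours of delivery".

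The primary endpoint is QBL at delivery, which section 3.3 makes the only basis of the primary analysis. Under Study Visit 2, QBL "will be calculated by the labor suite nurse". Nothing is said about whether that nurse knows the arm. Section 3.2 assigns the TA infusion to a different role, the research nurse.

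Section 4.5 says that data already collected are kept when a woman withdraws and that nothing more is collected. Section 3.3 asks for 20 evaluable women and plans descriptive comparisons only.

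**The concern.** Between screening and delivery, no study treatment depends on the arm, so the woman's care in the trial does not require her to know it. Telling her opens two routes for bias.

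- **Withdrawal.** The risk/benefit text in section 4.3 describes the combination as possibly more effective and rVWF alone as the standard. A woman who learns weeks ahead that she is in Arm B has a reason to leave that a woman in Arm A does not. If she leaves before delivery, her primary endpoint is never collected. The plan gives no analysis set, replacement rule or allowance for loss after randomization.
- **Care and measurement.** If the arm is known before labour, it may influence how the delivery is managed and how QBL is recorded. Blood lost before TA is given cannot be reduced by TA, so an arm difference in that part of QBL can only be chance or bias.

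The stated primary objective is efficacy on QBL, and section 3.2 says that a feasible pilot leads to a large multicenter phase III trial. A weakness here could be carried forward.

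**Working it through.** **1. The plan's own figure.** Section 3.3 gives 20 evaluable women, and the Dosing Schema gives 10 + 10 = 20. No significance level, power, effect size, SD or dropout rate is stated, so the 20 cannot be reproduced by a formula. Up to 30 are screened to enrol 20, and section 4.5 counts a woman as enrolled once screening assessments are complete. The 30 therefore covers screening losses, not losses after randomization.

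**2. How long before the arms differ is the arm disclosed?** Four sources bear on this.

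- Schedule: Week 0 minus Week -4 = 4 weeks.
- Participation: "The duration of the study for each subject will be up to 8 weeks", and for the last visit "The visit occurs at 21 days postpartum, at the end of study". Taking 21 days as 3 weeks, the longest gap that fits is 8 - 3 = 5 weeks. The synopsis gives 4 weeks of follow-up, which leaves 8 - 4 = 4 weeks.
- Screening text: "baseline laboratory studies within 3 weeks of the escalating dose study". This trial has no dose escalation. If the phrase means the first study dose, it suggests 3 weeks.
- Screening window: gap = gestation at delivery - 32. Gestation at delivery is not stated and must be assumed: 37 - 32 = 5 weeks, 40 - 32 = 8 weeks, 42 - 32 = 10 weeks. For a woman screened at 39 weeks who delivers at 40, the gap is 1 week.

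The 8-week case does not fit the stated participation: 8 weeks before delivery plus 3 after makes 11, against a stated maximum of 8. About 4 weeks is the documents' own figure.

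**3. What does a withdrawal cost?** One woman of 10 is 1/10 = 10% of an arm. The documents give no withdrawal rate, so the rate d below is assumed.

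| Assumed d | Evaluable of 20: 20(1 - d) | Chance none lost: (1 - d)^20 | Randomized for 20 evaluable: 20/(1 - d), rounded up |
|---|---|---|---|
| 5% | 19 | 36% | 22 |
| 10% | 18 | 12% | 23 |
| 15% | 17 | 4% | 24 |
| 20% | 16 | 1% | 25 |

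These figures cover loss for any reason. They do not show that loss would depend on the arm.

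**4. How far could selective loss move an arm mean?** As a worst case, suppose that the k women with the highest QBL leave one arm of 10. QBL is assumed normal, and the shift comes from 400,000 simulated arms. In SD units, the standard error of the difference is sqrt(1/10 + 1/(10 - k)).

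| k lost | Shift in arm mean (SD) | Standard error of difference (SD) | Shift / standard error |
|---|---|---|---|
| 1 | 0.17 | 0.459 | 0.37 |
| 2 | 0.316 | 0.474 | 0.67 |
| 3 | 0.455 | 0.493 | 0.92 |

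Women deciding before delivery do not know their QBL, so perfect selection of this kind is not realistic. Under the normal assumption these are ceilings, not estimates.

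**5. Who needs the arm, and when?** rVWF is the same for everyone, so giving the dose at delivery or epidural does not require the arm. The first step that does is TA. The data centre randomizes and the pharmacy supplies drug by randomization code (section 3.1), the research nurse infuses, and the labor suite nurse calculates QBL (section 3.2). The roles needed to hold the allocation back already exist.

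**6. When is randomization?** Study Visit 1 and the Appendix put it at screening. The Screening Procedures sentence can be read as putting it at delivery, or as describing treatments that are given at delivery. Inclusion criterion 4 has the same ambiguity.

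**The case against.** The strongest reply is that the trial is openly unblinded, compares the arms descriptively, plans no hypothesis test and justifies its size by feasibility, so when participants learn their arm is largely a matter of preference. Part of this stands: it limits the consequence. It does not remove it, because the primary objective is worded as efficacy and a descriptive mean is distorted by selective loss just as a tested one is.

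A second reply is that the text tells only the woman. That is correct. A reader might infer that the labor suite nurse is told the arm too; the documents do not say so, and they give the infusions to a different nurse. What stands is that nothing keeps the QBL nurse unaware in an open-label trial.

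A third is that no effect of disclosure on withdrawal or care is shown. This is also correct: the documents contain no withdrawal rate and no evidence that care differs by arm.

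A reader might also think that the cleanest remedy is to hold the allocation until QBL has been recorded. That would damage the trial. TA is the only difference between the arms, so wherever it was followed, the whole primary endpoint would precede TA and could say nothing about it. It could also shift when TA is given.

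**Conclusion.** The point holds as an avoidable risk with a cheap remedy. The arm is disclosed about 4 weeks before the arms differ, by the protocol's own schedule. In a trial with 10 women per arm and one primary endpoint, each pre-delivery withdrawal removes 10% of an arm, and nothing in the plan keeps the person calculating QBL unaware of the arm.

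Two stronger readings are tempting and not supported. The first is that disclosure precedes treatment by 8 weeks. In the protocol, 8 weeks is total participation; as a gap it needs screening at 32 weeks and an assumed delivery at 40, and it then conflicts with the stated participation. The second is that bias or differential withdrawal is present. The shifts of 0.17 to 0.455 SD are worst cases under assumed normality and perfect selection, and each is smaller than the standard error of the difference.

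The two statements on the time of randomization may be loose wording rather than a true contradiction, but they need to agree.

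**What to change.** 1. In section 3.2, Study Visit 1, delete the clause that has the woman informed of her group. Randomization may stay at screening.
2. State that the data centre and research pharmacy hold the allocation until delivery and disclose it to the research nurse only when it is needed to give the assigned study drug. The protocol's TA timing stays as written, and release is not tied to completion of QBL.
3. State that the labor suite nurse who calculates QBL is not told the arm.
4. Reconcile the Screening Procedures sentence on randomization with Study Visit 1 and the Appendix.

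Cost: a few lines of text and a pharmacy release at delivery. The woman no longer knows her arm in advance.

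Limits: women may still withdraw before delivery, but not because they know their arm. The QBL nurse may infer the arm once TA is given. The pictorial blood loss chart, which the woman scores herself in her diary, remains unblinded.

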This is a prospective, randomized single-center phase III pilot clinical trial comparing recombinant von Willebrand factor (rVWF, Vonvendi®) plus tranexamic acid (TA, Cyclokapron®) vs. rVWF alone to reduce postpartum hemorrhage (PPH) in women with von Willebrand disease (VWD). We *hypothesize* that intravenous rVWF given just before delivery plus intravenous tranexamic acid within 3 hours of delivery is superior to rVWF alone in reducing postpartum blood loss.

Objective:

The **Primary Objective** is to determine the efficacy of rVWF plus TA vs. rVWF alone in reducing postpartum hemorrhage in women with VWD.

The **Secondary Objectives** are to evaluate safety, tolerability, and mechanism of rVWF plus TA vs. rVWF alone in reducing PPH in women with VWD.

Endpoints:

The **Primary Endpoint** is quantitative blood loss (QBL) calculated by a labor suite nurse at delivery. The **Secondary Endpoints** include safety assessment by lochial blood loss by pictorial blood assessment chart (PBAC), blood products, transfusion, and hysterectomy within 21 days of delivery; and mechanism of PPH reduction by VWF assays, fibrinogen, and d-dimer.

Study Population:

Study subjects will be females age \geq 18 years of age with von Willebrand disease, defined by VWF:RCo <0.50 IU/dL (historic) and previous bleeding history, undergoing vaginal or caesarean section delivery. A total of 20 eligible subjects with VWD will be enrolled in this 2-year trial.

Site Enrolling Subjects:

Pilot: Participating site is HCWP, and Magee Hospital obstetricians.

Description of Study Intervention:

There are two study interventions: rVWF plus tranexamic acid vs. rVWF alone. Recombinant von Willebrand factor (rVWF, Vonvendi®) is an FDA-approved clotting factor approved for treatment or prevention of bleeds including postpartum hemorrhage hemorrhage in VWD. It is an intravenous agent administered in single-use vials containing approximately 650-1300 IU per vial as a sterile, lyophilized powder. The vials are reconstituted with 5-10 ml vial of sterile water for injection, USP, which is transferred by two-way needle into the lyophilized powder for reconstitution, and the reconstituted vial infused over 5-10 minutes, at 80 IU/kg (per pre-pregnancy weight) at delivery (or epidural), and days 1 and 2 postpartum.

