Why there is increased blood loss and lower VWF levels at delivery in women with VWD, despite VWF treatment, remains unknown. The current recommended VWF dosing, 50 IU/kg, does not take into account the 1.5-fold increase in blood volume.²⁸ Yet, while not used in pregnant women with VWD, volume-based dosing, rather than weight-based factor dosing is routinely used in children and obese adults with hemophilia.²⁹ Yet, during pregnancy, the physiologic increases in cardiac output, extracellular fluid, renal blood flow, and glomerular filtration rate accelerate drug clearance,^{30,31} and is the basis for blood volume-based dosing for a number of drugs in pregnancy.³² Finally, the physiologic fibrinolysis that occurs in the first three hours postpartum may contribute to greater bleeding in the woman with a bleeding disorder such as VWD.

Therefore, we *hypothesize* that rVWF 80 IU/kg IV, a dose safe and effective in treatment and prevention of VWD bleeding, standardly administered for surgery, and appropriate for the 1.5-fold increase in blood volume in pregnancy, when given before and on day 1 and day 2 after delivery, *plus* tranexamic acid 1 gm IV, a dose safe and effective in treatment and prevention of postpartum hemorrhage and mortality related to PPH, will be superior to rVWF alone in reducing PPH in women with VWD. This trial will help to enhance our understanding of the coagulopathy and mechanism PPH in VWD and, will be consistent with the goals and objectives of Healthy People 2020, to develop safer, more effective products for treatment of VWD.

2.2 Significance. By studying the safety and biologic effects of rVWF with TA vs. rVWF alone, we hope to

determine in this pilot study the feasibility of the VWD-Woman trial, the purpose of which is to reduce postpartum hemorrhage in women with VWD. Specifically, if we demonstrate the clinical hemostasis, and safety and tolerability of VWD with or without TA, in reducing PPH women with VWD, this would provide evidence that our clinical trial is feasible and biologically plausible. Finally, the findings of this study will potentially provide new information to determine feasibility for use in a future prospective phase III randomized clinical trial to prevent postpartum hemorrhage in women with von Willebrand disease, and promote blood product safety, consistent with the goals of Healthy People 2020.

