
3.3 Data Collection and Statistical Consideration.

This is a pilot study comparing rVWF + TA vs. rVWF alone in subjects with Von Willebrand disease, and therefore, comparisons between arms will be descriptive, including mean, median, standard deviation, frequency and percentages. A sample size of at least 20 subjects should provide be sufficient to determine feasibility of enrollment, study drug administration, and data collection for a future phase III trial. Data will be collected by [name] and her research nursing staff. All data required by the study will be adequately documented in the source documents (hospital records, clinical and office charts, laboratory reports, subject diaries, pharmacy dispensing records).

The Primary Objective is to determine the efficacy of rVWF plus TA vs. rVWF alone in reducing postpartum hemorrhage in women with VWD. The Primary Endpoint is quantitative blood loss (QBL) at delivery. The Secondary Objectives are to evaluate the safety, tolerability, and mechanism of rVWF plus TA vs. rVWF alone in reducing postpartum hemorrhage in women with VWD.

The Secondary Endpoints include safety assessment by lochial blood loss by pictorial blood assessment chart (PBAC) blood products, transfusion, and hysterectomy within 21 days of delivery; and mechanism of PPH reduction by VWF assays, fibrinogen, and d-dimer with 21 days of delivery.

Analysis of endpoints. The Primary Endpoint is based solely on quantitative blood loss (QBL) at delivery obtained by the labor suite nurse and documented by hospital chart. The Secondary Endpoints are based on assessments of safety and the mechanism of hemostasis by rVWF and/or TA. Safety variables, including lochial blood loss by PBAC, blood products, transfusions, and other medications; and the mechanistic variables, including VWF assays (VWF:RCo, VWF:Ag, FVIII:C) and coagulation assays (fibrinogen and d-dimer) will be assessed at 1 day, 2 days, and 21 days postpartum, and where possible, compared with assessment at screening.

Descriptive statistics will be provided for the primary efficacy variable and secondary safety and mechanistic assessment variables, and also by treatment arms. The frequency distribution of the hemostatic and safety efficacy assessments will be presented for each of the study arms.

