The subjects will be under close supervision during the study period. After administration of rVWF or TA it is anticipated postpartum bleeding frequency will be decreased from the untreated state. For women with VWD, it is already established rVWF and TA may reduce postpartum bleeding, but whether one agent is more effective or better tolerated than the other is not known.

Risk Benefit Ratio

The risk/ benefit ratio indicates the value of the information to be gained outweighs the potential risks of participation in the trial as 1) risks associated with rVWF and TA are low, importantly thrombosis risk is <0.4% with VWF, based on data from the literature; and 2) individuals with cardiac disease, hypertension, MI, stroke, thrombosis, or seizure are excluded from the trial. Thus, the risk/benefit ratio of participating in the trial outweighs the risk of gained outweighs the potential risks of participation in the trial.

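### The primary objective and superiority hypothesis promise a determination of efficacy that a descriptive comparison of 10 women per arm cannot give, and feasibility is not among the formal objectives

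*Combined protocol and SAP*

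**What the plan says.** **Objective and endpoint.** Section 3.3, like the synopsis, reads: "The Primary Objective is to determine the efficacy of rVWF plus TA vs. rVWF alone in reducing postpartum hemorrhage in women with VWD". It continues: "The Primary Endpoint is quantitative blood loss (QBL) at delivery". The secondary objectives are also comparative: "The Secondary Objectives are to evaluate the safety, tolerability, and mechanism of rVWF plus TA vs. rVWF alone".

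**Hypothesis.** The synopsis hypothesises that the combination "is superior to rVWF alone in reducing postpartum blood loss". Section 2.1 repeats that it "will be superior to rVWF alone in reducing PPH in women with VWD".

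**Analysis.** Section 3.3 says that, because this is a pilot, "comparisons between arms will be descriptive, including mean, median, standard deviation, frequency and percentages". No test, confidence interval, significance level, target difference or SD is given anywhere.

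**Size.** The dosing schema in section 3.2 shows 10 women in Arm A and 10 in Arm B.

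**Other statements of purpose.** Section 2.2 hopes to "determine in this pilot study the feasibility of the VWD-Woman trial". Section 3.2 gives the goal as preliminary information on safety and efficacy, and makes the large multicentre trial conditional on feasible procedures. Section 3.3 justifies the 20 subjects by feasibility. Its sample-size paragraph adds two criteria: success if no more than 6 of the 20 treatments are judged ineffective or unsafe, and feasibility if procedures can be carried out. Feasibility appears in neither the primary nor the secondary objectives, nor in section 1.0, Objective and Specific Aims.

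**The concern.** An objective is what the final report is held to. This one asks for a determination of efficacy under a superiority hypothesis, while the analysis section describes two small groups and supplies no measure of uncertainty. A report written to the objective could present a chance gap between the arms as efficacy, or a small gap as evidence that TA adds nothing. The data would support neither statement.

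Meanwhile the question that sets the sample size and governs the next trial, feasibility, is not among the objectives. Section 7.0 commits the sponsor to registering the trial and submitting its results, so the objectives and the primary endpoint shape what is made public.

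**Working it through.** **1. The plan's own figure.** The stated size is 20. It cannot be reproduced as a power calculation, because it rests on a rule of thumb (at least nine subjects for a pilot) with no significance level, effect size or SD. The plan's claim of adequate power is attached to judging success and feasibility, not to the comparison between arms.

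**2. Precision for QBL, the primary endpoint.** Inputs: 10 per arm (section 3.2). Assumed: all 20 women contribute a QBL value, values are roughly normal, and the arms share an SD.
- 95% half-width = t(0.975, 18 df) × √(2/10) × SD = 2.101 × 0.447 × SD = 0.94 SD.
- The documents give no SD. For assumed SDs of 200, 300, 400, 500 and 600 mL the half-width is 188, 282, 376, 470 and 564 mL.

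**3. Detectable difference.** This is illustrative, because no test is planned. Assumed: two-sided 5%.
- Normal approximation for 80% power: (1.960 + 0.842) × √(2/10) = 1.25 SD.
- Noncentral t, which suits this sample size: 1.32 SD.
- One-sided 5% (noncentral t): 1.16 SD.

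| True difference | Power, 10 per arm (t) | Per arm for 80% power (t) |
|---|---|---|
| 0.5 SD | 18.5% | 64 |
| 0.8 SD | 39.5% | 26 |
| 1.0 SD | 56.2% | 17 |

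**4. How often chance alone shows a gap.** With no true effect, the difference in means has standard error 0.447 SD. A gap of at least 0.5 SD in either direction has probability 2 × [1 − Φ(0.5/0.447)] = 2 × [1 − Φ(1.118)] ≈ 26%. Means and SDs listed by arm would not tell the reader this.

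**5. Secondary check on the PPH rate.** The objective is worded in terms of PPH, although the primary endpoint rests on QBL alone. Section 2.1 cites a PPH rate of at most one-third despite factor replacement, and an incidence of 5.5% in VWD. Exact Fisher power, 10 per arm, two-sided 5% (assumed):
- one-third to one-sixth: 4%;
- one-third to essentially zero: 21%;
- 5.5% to 2.75%: effectively zero.

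**6. The success rule.** The limit of 6 in 20 pools the arms. Three failures in each arm, or six in one arm and none in the other, both total 6 of 20 and both count as success. The rule therefore carries no information on adding TA. It is met with probability 91% at a true failure rate of 20%, 61% at 30% and 25% at 40%, whichever arm the failures fall in.

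**The case against.** The strongest defence is that the plan already limits itself. It calls the trial a pilot, gives that as the reason for describing rather than testing, and in section 3.2 sets a goal of preliminary information. No p-value is planned, so a false claim of efficacy would depart from the analysis section rather than follow from it. This stands in part. Descriptive analysis suits a pilot, and the analysis section makes a misleading claim less likely. But the formal objective and hypothesis still say something different from section 3.2, and the objective is the text that a report is measured against.

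Some stronger readings are tempting, and the documents do not support them.
- A reader might infer that feasibility is missing from the plan. It is not: it is a stated hope in section 2.2, the condition for the large trial in section 3.2, and the sample-size rationale and a criterion (without thresholds) in section 3.3. What is missing is its place among the objectives.
- A reader might infer that feasibility is the trial's only true purpose and must become the primary objective. Sections 3.2 and 3.3 also seek early information on safety and efficacy. The aims are mixed, and their ranking is for the sponsor.
- A reader might infer that the pilot needs a significance test or more women. The mismatch lies in the objective and hypothesis, and changing those removes it.

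The power figures concern a test that nobody proposes, so they illustrate the limits of the data and are not failures of a stated calculation.

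**Conclusion.** The point holds as a mismatch between the stated objective and the design. The objective and hypothesis claim a determination of efficacy and superiority. The design gives a comparison of 10 with 10, described without an interval, and the plan's own section 3.2 claims only preliminary information. The size of the gap is a 95% interval of about ±0.94 SD for the QBL difference, and about 1.32 SD needed for 80% power.

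The interval figure assumes complete data, rough normality and equal SDs. The power figure also assumes a two-sided 5% t-test. The documents state no significance level, SD or effect size, but the conclusion does not turn on these choices: a one-sided 5% test would still need 1.16 SD. It is worth correcting before results are reported. It does not undermine the pilot as a pilot.

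**What to change.** 1. In the synopsis and section 3.3, reword the efficacy objective as obtaining a preliminary estimate of the QBL difference between arms. Align sections 1.0, 2.1 and 3.2 with it.
2. In section 3.3, add that this difference is reported with a 95% confidence interval, and that the pilot will make no claim of efficacy, superiority or absence of effect.
3. In the synopsis and section 2.1, present superiority as the hypothesis of the later multicentre trial.
4. List feasibility (recruitment, randomisation, drug administration, data collection) as a formal objective, primary or co-primary as the sponsor prefers.
5. In the sample-size paragraph of section 3.3, state that the pooled rule of at most 6 in 20 is not evidence on the effect of adding TA.

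The cost is wording in several sections, one added interval, a matching registry entry and a weaker stated claim. No patients, visits or procedures are added.
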